2.1.1.3 Post baseline measurement

Post baseline measurements are defined as those assessments after the start of study treatment.

2.1.1.4 Change from baseline

When change from baseline is of interest the following formula will be used for each scheduled visit and time-point where baseline and post-baseline values are both available:

Change from baseline = post-baseline value – baseline value; and

If baseline or post-baseline values are missing, then the change from baseline will be missing.

2.1.1.5 Completion and last contact

A patient will complete the core treatment period when the patient has completed the Day 168 visit in the study or EOS for participants who discontinue from the study prior to the extension treatment period. The maximum of the date of last visit in the core treatment period, date of withdrawal of consent (in case of withdrawal from study), would be the date of last contact for the patient in the core treatment period.

2.2 Analysis sets

The **Screening set (SCR)** consists of all patients who have been screened. If a patient has been screened multiple times then the patient should be included for his/her last screening.

In Section 12.1 of Study protocol, the **Enrolled Set (ES)** comprises all participants enrolled in the study, which is equivalent to the **Screening set (SCR)**.

The **Full Analysis Set (FAS)** comprises all participants with confirmed eligibility to whom study treatment has been assigned. This will be the data set used for analysis of all efficacy endpoints.

The **Safety Set (SAF)** includes all participants who received at least one dose of study treatment.

2.3 Patient disposition, demographics and other baseline characteristics

Demographic and other baseline data including disease characteristics will be summarized descriptively for the FAS. In addition, summaries of relevant past or current medical conditions will be presented.

Categorical data will be presented as frequencies and percentages. The summary statistics shown for continuous data will be mean, standard deviation, median, minimum, and maximum.

2.3.1 Patient disposition

Core treatment period

The number of patients screened, screened but not treated, treated, completed and discontinued from the study in the core treatment period will be summarized. The reasons for screen failure will be provided. Participants discontinued from the study in the core treatment period will also be summarized with reasons for discontinuation. In addition, number of participants who discontinued study treatment, reason for discontinuation of study treatment and number of patients who discontinued study treatment but stayed in the core treatment period will be summarized. Participants who discontinued study treatment but continued in the study during the core treatment period are defined as participants with the date of study discontinuation or Day 168 visit - the end date of study treatment > 0.

Extension treatment period

The number of participants who completed and discontinued from the study in the Extension treatment period will be summarized. The reasons for discontinuation will be provided.

The number of subjects with protocol deviations, including those due to COVID-19, will be tabulated by deviation category and deviation for the FAS.

Based on FAS, the number of participants enrolled by country will be presented.

2.3.2 Relevant Medical History and current medical conditions

Medical history will be coded using the Medical Dictionary for Regulatory Activities (MedDRA) terminology using the most recent version at the time when the last participant has completed the core treatment period. Medical history terms will be summarized by primary system organ class and preferred term. Hemoglobin history prior to screening (defined as mean result for hemoglobin obtained over a minimum of 6 months prior to screening), disease duration (as derived from the start date of PNH in Medical History page up to the date of screening) will be summarized separately.

History of MAVE (MAVEs prior to screening) will be summarized by medical history term. Transfusion history (the numbers of transfusions and unit numbers of packed-RBC received in the last 12 months prior to screening), transfusions up to 6 months prior to starting study treatment (yes, no) will be presented.

Vaccination history will be presented by serogroup/polyvalent.

Alcohol history will be reported based on usage (never, current, former). Smoking and vaping history will be presented based on type of substance (e-liquids, tobacco) and usage (never, current, former).

All the summaries will be presented on FAS.

2.4 Treatments (study treatment, rescue medication, concomitant therapies, compliance)

2.4.1 Study treatments

Treatment of interest

The investigational drug LNP023 (iptacopan) as 200 mg capsules, will be prepared by Novartis and supplied to investigator sites as open-label participant packs

Duration of treatment in the core treatment period

The duration of treatment iptacopan 200 mg b.i.d in the core treatment period is defined as the duration from the date of first administration of study treatment in the core treatment period to the date of last administration of iptacopan (any dose) in the core treatment period.

The end of the core treatment period is the date of last administration (any dose) in the core treatment period.

Duration of treatment in extension treatment period

The duration of iptacopan 200 mg b.i.d treatment in extension treatment period will be defined as the duration from the first date of administration of iptacopan 200 mg b.i.d in the day after Day 168 or the first administration of iptacopan 200 mg b.i.d in the extension treatment period to the date of last administration of iptacopan 200 mg b.i.d in the extension treatment period.

Overall duration of treatment

An overall duration of iptacopan 200 mg b.i.d treatment would include both core treatment period and extension treatment periods, with a start date and a stop date as described above for core treatment period and extension treatment periods, respectively.

Exposure and Dose Intensity for iptacopan

The Safety set (SAF) will be used for the analyses of exposure to iptacopan described below. Categorical data will be summarized as frequencies and percentages. For continuous data, mean, standard deviation, median, 25th and 75th percentiles, minimum, and maximum will be presented.

The duration of exposure (in days) to iptacopan as well as the dose intensity and the relative dose intensity of iptacopan 200 mg b.i.d will be summarized by means of descriptive statistics using SAF during the core treatment period and for overall.

Duration of exposure to study treatment will be calculated as the number of days between the first dose date and the last dose date exposed to Iptacopan 200 mg b.i.d over the specified period but excluding temporary treatment interruptions (expressed as: Duration of exposure = Date of last known dose of study drug – Date of first dose of study drug + 1 excluding interruptions).

The duration of exposure to study treatment will be computed and summarized as the duration of treatment, but excluding temporary treatment interruptions. To establish the start of an interruption, the same rules should apply as for end of the duration of treatment described above.

An interruption will be defined as at least one full day without any dose.

Cumulative duration exposure on iptacopan 200 mg b.i.d based on SAF will be summarized as a categorical variable classified into ≤ 4 , ≤ 8 , ≤ 12 , ≤ 16 , ≤ 20 , ≤ 24 , ≤ 28 , ≤ 32 , ≤ 36 , ≤ 40 , ≤ 44 , ≤ 48 weeks.

The duration of exposure will be the basis for the computation of the dose intensity and the relative dose intensity. The dose intensity for patients on iptacopan 200 mg bid will be computed as the ratio of actual cumulative dose received and actual duration of exposure. Relative dose intensity for patients on iptacopan 200 mg b.i.d will be computed as the ratio of dose intensity

and planned dose intensity. The planned dose intensity for patients on iptacopan 200 mg bid will be 400 mg/day. The dose intensity for patients on iptacopan will be summarized as a categorical variable classified into the categories stated in [Table 2-1](#). Relative dose intensity will also be summarized on a continuous scale as well as considering categories (%): ≤ 75 , > 75 , > 90 -100 and summaries on dose intensities will be presented on SAF.

The information on iptacopan +transfusions will be summarized as a categorical variable considering the dose intensity and transfusions in the core treatment period. Summaries on the categories stated in [Table 2-1](#). Such summaries will be presented on SAF.

For participants on iptacopan, the calculation of duration of treatment, exposure, dose intensity and relative dose intensity will include the investigational treatment iptacopan 200 mg b.i.d as well as the iptacopan tapering doses (if applicable).

Table 2-1 Summary on dose intensity and transfusions for patients on iptacopan

Dose intensity	Dose intensity and transfusions
<400 mg/day	<400 mg/day + no transfusion
400 mg/day	<400 mg/day + 1 transfusion
	<400 mg/day + ≥ 2 transfusions
	400 mg/day + no transfusion
	400 mg/day + 1 transfusion
	400 mg/day + ≥ 2 transfusions

For participants on iptacopan, an interruption will be defined as at least one full day without any dose. The number of participants with interruptions, number of interruptions and durations of interruptions will be summarized on SAF. The information on study medication intake for participants having at least one interruption will be listed. The number of participants with missed doses and number of missed doses will be summarized on SAF.

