Vaccinations should be completed as per Inclusion criteria (Section 5.1 in study protocol). To fulfill the hemoglobin and LDH eligibility criteria, participant will have two different samples collected during the screening period and tested by the central laboratory prior to starting study treatment. In case the participant has received a RBC transfusion following the initial Screening visit, the participant is eligible based on the initial central hemoglobin if $< 10\text{g/dL}$.

The absolute reticulocytes count will be measured at Screening to determine eligibility with regards to exclusion criterion # 6. Due to the kinetics of maturation of reticulocytes into mature red blood cells and turnaround time from reticulocytes sample collection and analysis by central laboratory, local reticulocytes testing can be performed at the same time as the central testing during the Screening period. In the event that the absolute reticulocytes count as assessed by the central laboratory during the Screening period is below the protocol defined threshold (absolute reticulocytes $< 100 \times 10^9/\text{L}$) and only in this scenario, the results from the local lab

testing can be used to determine participant's eligibility. The results of the local laboratory values (including reference ranges) should be included in the eCRF to document eligibility.

If eligibility criteria are not met due to any assessment, the participant should be considered as having failed the screening and cannot start study treatment. The participant can be re-screened as described in detail in Section 8.1 in study protocol.

Core treatment period

Participants who meet the eligibility criteria will proceed to the Core treatment period. Treatment with iptacopan at a dose of 200 mg b.i.d. will start on the first day (Day 1) and continue for 24 weeks with study visits and corresponding assessments according to the schedule described in Table 8-1 of CLNP023C12301 clinical study protocol.

The Core treatment period will end with the completion of the Week 24 visit assessments. Upon completion of the Week 24 visit, participants may enter the Extension treatment period, as described below.

Extension treatment period

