1.2 Study objectives and endpoints

Table 1-1 Objectives and related endpoints for the Core treatment period

Objective(s)	Endpoint(s)
Primary Objective(s)	Endpoint(s) for primary objective(s)

 To assess the effect of iptacopan on proportion of participants treated with iptacopan achieving a sustained increase from baseline in hemoglobin levels of ≥ 2 g/dL in the absence of red blood cell transfusion 	
 Response defined as having an increase from baseline in Hb ≥ 2 g/dL assessed between Day 126 and Day 168, in the absence of packed red blood cell (pRBC) transfusions between Day 14 and Day 168
Secondary Objective(s)	Endpoint(s) for secondary objective(s)

 To assess the effect of iptacopan on the proportion of participants achieving 	
 Response defined as having Hb levels ≥ 12 g/dL between Day 126 and Day 168 in

Objective(s)	Endpoint(s)
sustained hemoglobin levels \geq 12 g/dL in the absence of red blood cell transfusions	absence of red blood cell transfusion between Day 14 and Day 168

 To assess the effect of iptacopan on transfusion avoidance (TA) defined as the proportion of participants who remain free from transfusions 	
 Absence of administration of packed-red blood cell transfusions between Day 14 and Day 168

 To assess the effect of iptacopan on average change in hemoglobin 	
 Change from baseline in hemoglobin (g/dL) as mean of visits between Day 126 and Day 168

 To assess the effect of iptacopan on average percent change in Lactate Dehydrogenase (LDH) 	
 Percent change from baseline in LDH levels (U/L) as mean of visits between Day 126 and Day 168

 To assess the effect of iptacopan on the rate of breakthrough hemolysis (BTH) 	
 Occurrences of breakthrough hemolysis reported between Day 1 and Day 168

 To assess the effect of iptacopan on average change in reticulocyte counts 	
 Change from baseline in reticulocyte counts ($10^9/L$) as mean of visits between Day 126 and Day 168

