
 To assess the effect of iptacopan on improving fatigue, using the FACIT-Fatigue questionnaire 	
 Change from baseline in FACIT-Fatigue scores as mean of visits between Day 126 and Day 168

 To assess the rates of Major Adverse Vascular Events (MAVEs incl. thrombosis) 	
 Occurrences of MAVEs occurring between Day 1 and Day 168

 To assess safety and tolerability of iptacopan 	
 Safety assessments (including adverse events/serious adverse events, safety laboratory parameters, vital signs etc.) between Day 1 and Day 168

[figure not shown]

Table 1-2 Objectives and related endpoints for the Extension treatment period

Objective(s)	Endpoint(s)

 To assess long term safety, tolerability and efficacy of iptacopan 	
 Safety assessments including adverse events/serious adverse events, safety laboratory parameters, vital signs etc. through End of Study visit Efficacy endpoints including hematological response parameters, transfusion avoidance, BTH, FACIT-fatigue score, MAVEs through End of Study visit

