1.2.1 Primary estimands

The primary clinical question of interest is:

What is the effect of iptacopan, regardless of discontinuations of study drug or occurrence of Breakthrough hemolysis (BTH) or Major Adverse Vascular Events (MAVEs) on the primary endpoint (a composite of improvement in hemoglobin levels and absence of RBC transfusions), as assessed by the proportion of responders?

This primary estimand captures both the hematological effect of the study drug (as evaluated by a clinically relevant increase of ≥ 2 g/dL in hemoglobin levels) and the absence of RBC transfusions after Day 14 which are regarded as treatment failure.

The attributes of the primary estimand are:

- Population: PNH Patients ≥ 18 years old with hemolysis (LDH > 1.5 ULN) and anemia (hemoglobin < 10 g/dL), and who have not received any complement inhibitor therapy (including anti-C5 antibody).
- Treatment of interest: the investigational treatment iptacopan at a dose of 200 mg b.i.d regardless of whether the patient discontinues treatment (treatment policy).
- Intercurrent events: Transfusions (after Day 14) will be considered treatment failures and as such captured in the endpoint. Discontinuations of study medication for any reason, BTH events, and MAVEs will be handled with a treatment policy strategy.
- The summary measure: the probability of being a responder, standardized to the population of patients assigned to iptacopan in this study.

The justification of handling of intercurrent events is in [Table 1-3](#). The overview of estimands and estimation methods is in [Table 5-1](#) in [Section 5.2](#).

Table 1-3 Justification of handling of intercurrent events

Intercurrent event	Handling strategy	Justification
Discontinuation of study medication	Treatment policy	The effect of treatment will be assessed even when participants discontinue study medication. Data collection will be maintained and available measurements post-treatment discontinuation used maintaining the treatment label as assigned at enrollment.
Breakthrough hemolysis events	Treatment policy	The effect of treatment will be assessed. Breakthrough hemolysis may affect the endpoints considered in the study, hence data collection will be maintained and available measurements collected after breakthrough hemolysis event keeping the treatment label as assigned at enrollment.

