2.6.1.7 Rates of Major Adverse Vascular Events (MAVE)

Information of MAVEs as collected on the 'MAVE' CRF page will be used for analysis and the information will also be reported as a part of the adverse event summaries. The number and percentage of participants with treatment-emergent (MAVEs) in the core treatment and extension treatment periods will be summarized by reported term. The information on MAVEs (including those in the screening period) will be listed and the treatment emergent events will be flagged.

Based on FAS, the estimation of rates of MAVEs will be carried out using a negative binomial model. Due to the expected low frequency of occurrences, no covariates are planned to be included. Following the treatment policy strategy for handling treatment discontinuations, the offset variable will be defined as the time from Day 1 till minimum (end of study, end of core treatment period).

If the model fails to converge, then a Poisson model without covariates will be fitted. If both negative binomial and Poisson model fail to converge, the Wilson ([Miettinen and Nurminen, 1985](#)) method will be implemented to produce 95% CI.

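### SAP 2.4.1 misstates the end of the core treatment period as the last dose; used literally in the BTH and MAVE offsets, it would drop follow-up after stopping (minor)

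*SAP*

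**What the plan says.** SAP 2.4.1, in the paragraph on duration of treatment, says: "The end of the core treatment period is the date of last administration (any dose) in the core treatment period".

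Three other places in the SAP place the end of the period elsewhere:

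- SAP 1.1: "The Core treatment period will end with the completion of the Week 24 visit assessments".
- SAP 2.1.1.5: "A patient will complete the core treatment period when the patient has completed the Day 168 visit in the study or EOS", the EOS alternative being for those who leave the study before the extension.
- SAP 2.3.1: the "number of patients who discontinued study treatment but stayed in the core treatment period will be summarized".

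The term then appears in the rate models. For MAVEs (SAP 2.6.1.7), "the offset variable will be defined as the time from Day 1 till minimum (end of study, end of core treatment period"). SAP 2.6.1.8 repeats this for BTH. Both sentences open by saying that they follow the treatment-policy strategy for discontinuation.

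The endpoints in SAP 1.2 are "Occurrences of breakthrough hemolysis reported between Day 1 and Day 168" and "Occurrences of MAVEs occurring between Day 1 and Day 168". SAP 1.2.2 gives both summary measures as occurrences per year. On stopping treatment, Table 1-3 in SAP 1.2.1 says: "Data collection will be maintained and available measurements post-treatment discontinuation used maintaining the treatment label as assigned at enrollment".

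**The concern.** The SAP gives one period two different ends. Under the 2.4.1 sentence, the group that SAP 2.3.1 sets out to count would be empty.

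The conflict matters beyond wording because the same term closes the offset in two rate models. A programmer who looked the term up in 2.4.1 would stop a participant's person-time at the last dose. The numerator would not stop there: the estimands count events to Day 168, and the rate models do not restrict events to treatment-emergent ones (that restriction is attached only to the descriptive counts and listing flags). Protocol 9.1.1 asks participants who stop to keep attending visits to Week 24, so events after stopping would be recorded. Protocol 4.5 names hemolysis after discontinuation as a theoretical risk specific to PNH, so this is a stretch of follow-up in which events may occur.

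At stake is the size of two secondary rates, which would come out too high.

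**Working it through.** **The plan's own figures.** The documents state no BTH or MAVE rate, person-time or discontinuation rate, so there is no figure to reproduce for this point. The sample-size statements in SAP 3 concern the responder proportion and contain no person-time.

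**Inputs.** N = 40 (SAP 3). Event window of 168 days (SAP 1.2). 365.25 days per year (the convention in SAP 2.7.1). Assumed: d participants take their last dose on day s, and all 40 are followed to Day 168.

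**Formulas.**

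- Intended person-time = 40 × 168 / 365.25 = 6720 / 365.25 = 18.398 years.
- Person-time with 2.4.1 used literally = ((40 − d) × 168 + d × s) / 365.25.
- The crude rate is events divided by person-time, so it is inflated by 6720 / (6720 − d × (168 − s)), whatever the number of events.

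| d | s | Literal person-days | Literal person-years | Ratio |
|---|---|---|---|---|
| 0 | – | 6720 | 18.398 | 1.000 |
| 1 | 140 | 6692 | 18.322 | 1.004 |
| 1 | 84 | 6636 | 18.17 | 1.013 |
| 2 | 98 | 6580 | 18.015 | 1.021 |
| 2 | 84 | 6552 | 17.938 | 1.026 |
| 4 | 84 | 6384 | 17.48 | 1.053 |
| 4 | 28 | 6160 | 16.865 | 1.091 |

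The row with s = 98 is a stop at Day 84 followed by the 14-day taper in protocol 9.1.1; because 2.4.1 counts any dose, the taper moves the last dose later. Over 1 to 4 stoppers between Day 28 and Day 140, the omitted person-time is 0.08 to 1.53 of 18.40 years and the ratio is 1.00 to 1.09. A more extreme assumption, 8 of 40 stopping at Day 28, gives 5600 person-days and a ratio of 6720 / 5600 = 1.20.

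**Illustrative rates (d = 2, s = 84; event counts assumed).**

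- 4 BTH events: 4 / 18.398 = 0.217 per year intended; 4 / 17.938 = 0.223 literal.
- 1 MAVE: 1 / 18.398 = 0.054 intended; 1 / 17.938 = 0.056 literal.

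**Model check.** An intercept-only negative binomial fit to the BTH example (two completers and two stoppers with one event each) gives 0.2174 and 0.2229, ratio 1.026. An intercept-only Poisson fit with 3 events and 4 participants stopping at Day 84 gives 0.163 and 0.172, matching the tabled 1.053. The planned BTH model has covariates, so its ratio need not equal the crude one exactly.

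**The case against.** A reader might infer that the SAP plans an on-treatment denominator for these rates. The documents do not support that:

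- SAP 2.6.1.7 and 2.6.1.8 do not cite 2.4.1. Where the SAP wants a 2.4.1 definition it says so, as SAP 2.4.2 does for concomitant therapy.
- The offset sentences begin with the treatment-policy strategy, and ending person-time at the last dose is the opposite of it.
- The minimum with end of study would do nothing if the core period ended at the last dose, since a last dose in the study cannot fall after the end of study. It has a purpose only if the period ends around Day 168.
- The 2.4.1 sentence is circular: it speaks of the last dose within the core period, so it presupposes a boundary set elsewhere, and SAP 1.1 sets one. It sits in an exposure paragraph, and SAP 2.4.2 refers to the end of treatment with the same any-dose qualifier, which is probably what 2.4.1 meant.

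The effect is also small beside the sampling error. Exact Poisson 95% intervals are about 0.06 to 0.56 per year for 4 events in 18.40 person-years and about 0.001 to 0.30 for 1 event, against shifts of about 0.006 and 0.001. The error raises event rates, so it works against iptacopan, and no threshold or test is attached to these rates.

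All of this stands, and it makes the bias a risk of literal reading only. It does not rescue the 2.4.1 sentence, which is current text and wrong as written. A reader should not have to work out from the structure of the offset sentence which of two stated ends applies.

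**Conclusion.** The 2.4.1 sentence is a wrong stated definition, in conflict with SAP 1.1, 2.1.1.5 and 2.3.1. Its possible consequence is confined to the BTH and MAVE rates and arises only if a programmer applies 2.4.1 to the offsets against their evident intent. In that case the rates are inflated by about 0 to 9% for 1 to 4 of 40 participants stopping between Day 28 and Day 140 and followed to Day 168. The numbers and timing of stops are assumptions. With no early stoppers the effect is zero.

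Two further inferences would go too far. No events are lost: the numerator still runs to Day 168. Nor is the main efficacy conclusion touched: the primary endpoint, the 15% threshold and the sample size do not use this offset. The severity is minor, and the correction is worth making because it costs almost nothing.

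**What to change.** 1. **SAP 2.4.1.** Insert *treatment in* after *The end of*, so that the sentence dates the end of treatment in the core period and no longer the end of the period itself. This alone removes the contradiction.
2. **SAP 2.6.1.7 and 2.6.1.8.** Define the offset as the time from Day 1 to the earlier of end of study (including death) and Day 168, whether or not iptacopan has been stopped. State that the events analysed are those in that same interval.

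Use study Day 168 here, not the date of the Day 168 visit. Protocol Table 8-1 allows that visit 3 days either side, so a Day 165 visit would drop Days 166 to 168 and a Day 171 visit would add days outside the window in SAP 1.2.2.

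The cost is a wording edit in three SAP sections, with no new data, visits or outputs. The rates will include time off iptacopan, possibly on replacement therapy, which the treatment-policy strategy already intends.
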